6.2.2. Age

Age, in completed years, at screening will be calculated for each subject and will be defined as:

Age (years) = integer value ((Date of Screening - Date of Birth + 1) / 365.25).

6.2.3. Study Day

Study Day 1 is the day when a subject enters the treatment period. Study Day -1 is the day before the subject enters the treatment period, all assessments prior to study Day -1, including the Screening and Admission visits, will have negative study days.

If the date of interest occurs on or after the first study drug administration date, study day will be calculated as (date of interest - first study drug administration date + 1). If the date of interest occurs prior to the first study drug administration date, study day will be calculated as (date of interest - first study drug administration date).

6.3. MISSING DATA

There will be no imputation for missing data, unless otherwise specified.

AEs and CMs with incomplete start dates will be considered as treatment-emergent or prior/concomitant, respectively, according to the following algorithm:

1. If the AE occurrence type is specified for the AE on the eCRF, it will be used to determine treatment-emergence. This will be verified using the algorithms below (steps 3 through 5).
2. If a medication started and stopped prior to the start of study treatment, the medication will be considered prior. This will be verified using the algorithms below (steps 3 through 5).
3. Only the start year is reported: If the year is after or the same as the year of the first dose date, the event will be considered treatment-emergent.
4. Only the start month and year are reported: If the month/year is after or the same as the month/year of the first dose date, then the event will be considered treatment-emergent.

5. If the event occurred or medication was started on or after the date of the first dose date, then the event will be considered treatment-emergent.

The missing severity of an AE will be imputed to “severe”; the missing relationship to study drug of an AE will be imputed to “probably related”.

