8.2 Adverse Event Definitions

8.2.1 Adverse Events (Adverse Experiences)

Collection of systemic and cutaneous AEs will be initiated after the ICF has been signed and conclude when the post-study procedures are completed (or Early Discontinuation). This includes the time between screening and the first patch application.

An AE is any untoward medical event that occurs in a clinical investigation, where a subject is administered a medicinal (investigational) product or medical device, and which does not necessarily have a causal relationship between the event and the treatment. An AE can be any

unfavorable and unintended sign or symptom, including clinically significant abnormal laboratory result, concomitant illness, or worsening of an existing medical condition.

A Treatment Emergent Adverse Event (TEAE) is an event that emerges during treatment having been absent pre-treatment, or worsens relative to the pre-treatment state.

Abnormal laboratory tests that are clinically significant, as determined by the investigator, should be reported as AEs if:

- the test result is associated with accompanying symptoms;
- the test result requires additional diagnostic testing or medical/surgical intervention;
- the test result leads to discontinuation from the study, significant additional concomitant drug treatment, or other therapy;
- the test result is considered to be an AE by the investigator or sponsor.

Merely repeating an abnormal test, in the absence of any of the above conditions, does not constitute an AE. Any abnormal test result that is determined to be an error does not require reporting as an AE.

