11.2. ADVERSE EVENTS

All systemic and skin AEs, regardless of suspected causal relationship to the investigational products, will be reported. Subject assessed skin adverse events such as skin redness (erythema), skin swelling (edema), skin bruising, skin bleeding, skin itching and skin pain are collected through the eDiary and will also be recorded as adverse events in the eCRF.

All Adverse Events (AEs) will be coded using the Medical Dictionary for Regulatory Activities (MedDRA; version 20.0 or higher). Migraine headaches will not be captured as AEs.

All AEs will be listed by subject. The following listings of AEs will be provided:

- All AEs,
- Study-drug related AEs,
- Serious adverse events (SAEs),
- AEs leading to death, and
- Adverse events leading to study-drug withdrawal.

Only TEAEs will be included in summary tables. An Overview summary table of TEAEs will be produced showing the following categories:

- Any TEAE,
- Study-drug related TEAEs,
- Serious TEAEs,
- TEAEs leading to study-drug withdrawal, and
- TEAEs leading to death.

All TEAEs will be classified by system organ class (SOC) and preferred term (PT). Frequency count and the number of unique subjects of a TEAE will be tabulated by treatment received. For the number of unique subjects reporting, if a subject reported more than one AE that was coded to the same SOC or PT, the subject will be counted only once for that specific SOC or PT.

The following summaries of TEAEs will also be provided:

- TEAEs by SOC and PT,
- Study-drug related TEAEs by SOC and PT,

- Serious TEAEs by SOC and PT,
- TEAEs by maximum severity (mild, moderate, severe or missing) by SOC and PT, and
- TEAEs by strongest causality relationship (not related, possibly related, probably related, definitely related or missing) by SOC and PT.

For TEAEs presented by relationship to study treatment(s), the strongest relationship to study treatment(s) during the study will be presented for each subject if coded to the same SOC or PT. For TEAEs presented by severity, the worst severity during the study will be presented for each subject if coded to the same SOC or PT. TEAEs with missing causality will be counted as related. TEAEs with missing severity will be counted as severe. The same will be true in the individual summaries.

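### SAP 6.3's date rules for treatment-emergence omit the protocol's worsening limb and ignore the AE stop date, and no rule settles a conflict with the eCRF field

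*SAP*

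**What the plan says.** Protocol 8.2.1 gives a treatment-emergent adverse event (TEAE) two limbs: absent before treatment and emerging during it, "or worsens relative to the pre-treatment state". The same section starts AE collection at consent and expressly includes the time before the first patch, so pre-dose AEs will be in the database. Protocol 8.3 asks for onset and resolution dates for each AE.

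The SAP uses the term throughout but does not define it. Section 6.3 introduces its algorithm with the words "AEs and CMs with incomplete start dates will be considered as treatment-emergent or prior/concomitant, respectively". The AE steps are:

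- Step 1: "If the AE occurrence type is specified for the AE on the eCRF, it will be used to determine treatment-emergence". The result is then to be verified against steps 3 to 5.
- Step 3, year only: "If the year is after or the same as the year of the first dose date, the event will be considered treatment-emergent".
- Step 4, month and year: "If the month/year is after or the same as the month/year of the first dose date, then the event will be considered treatment-emergent".
- Step 5: "If the event occurred or medication was started on or after the date of the first dose date", the event is treatment-emergent.

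Step 2 concerns medications only. It classes a medication that started and stopped before treatment as prior, and SAP 7.5.1 repeats a stop-date rule for medications. AEs have no counterpart. SAP 11.2 adds: "Only TEAEs will be included in summary tables". It also provides a listing of all AEs. SAP 13 declares changes to efficacy endpoints and none to the TEAE definition.

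**The concern.** Long-term safety is the primary objective and there is no control arm, so the TEAE summary tables carry the main result. The rule that admits an AE to those tables should match the protocol's definition, and where the date steps decide, it does not.

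The two gaps act in opposite directions. Without a worsening limb, an event that the protocol counts can be left out, which favours the product. Without a stop-date check, an event known to be over before the first patch can be counted in, which goes against it. Step 1 does not reliably close either gap. Neither document defines the occurrence-type field, it applies only when completed, and it is checked against date steps that a worsening under its original start date cannot pass. Two programmers following the SAP could classify the same record differently.

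**Working it through.** There is no stated figure to reproduce, so the check applies the rule to test records.

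**Steps 3 to 5 on test records.** Assume a first dose on 20 March 2018 (an illustrative date) and a blank occurrence type.

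| Record | SAP step and result | Protocol 8.2.1 |
|---|---|---|
| (a) Starts 5 March, worsens after first dose, one record | Step 5: 5 March is before 20 March, not a TEAE | TEAE (worsened) |
| (b) Same worsening entered as a new record starting 25 March | Step 5: TEAE | TEAE |
| (c) Start known only as March 2018, ended 10 March | Step 4: same month, TEAE | Not a TEAE |
| (d) Start known only as 2018, ended 10 March | Step 3: same year, TEAE | Not a TEAE |
| (e) Start known only as February 2018, ongoing, worsens after first dose | Step 4: earlier month, not a TEAE | TEAE (worsened) |

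Records (a) and (e) are lost from the summary tables. Records (c) and (d) are wrongly admitted. Record (b) shows that the first error disappears if worsening is entered as a new record.

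**With the occurrence type completed.** Suppose (a) is flagged treatment-emergent on the eCRF. Step 1 makes it a TEAE, but verification by step 5 says it is not. The SAP does not say what happens next.

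**How easily step 4 is met by a pre-dose onset.** Screening takes up to 7 days and may be combined with the start of run-in, which lasts 14 to 21 days. Visit 3 therefore falls about 14 to 28 days after screening starts. First dose then waits for a qualifying attack. At 2 to 8 attacks per 28 days, the mean wait is 28/2 = 14 to 28/8 = 3.5 days, so the pre-dose window runs from about 14 + 3.5 = 17.5 to 28 + 14 = 42 days.

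Assume that onset is uniform over a window of W days and that first dose is uniform over the days of 2018. A first dose on day d of a month has min(d − 1, W) pre-dose days in that month. For W = 14, the sums over d are 329 for a 31-day month, 315 for a 30-day month and 287 for February. The share is (7 × 329 + 4 × 315 + 287)/(365 × 14) = 3850/5110 = 75%. The same count gives:

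| Window W (days) | Same month as first dose (step 4) | Same year (step 3): 1 − (W + 1)/730 |
|---|---|---|
| 14 | 75% | 98% |
| 21 | 64% | 97% |
| 28 | 52% | 96% |
| 35 | 42% | 95% |
| 56 | 26% | 92% |

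A pre-dose AE with a partial start date will therefore often meet step 3 or 4, and only a stop date could show that it was over. These are shares of onset days. They are not counts of misclassified AEs: the documents do not say how many AEs will have partial dates, how many of those will have ended before first dose, or how often the occurrence type will be blank.

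**The case against.** Several points on the other side are sound.

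- *The eCRF field comes first.* A reader might infer that the SAP classifies AEs by start date alone. Step 1 rules that out: the date steps decide only when the field is blank, or if verification is allowed to overrule it.
- *The list is a partial-date convention.* It sits under Missing Data and opens with incomplete start dates, and the protocol definition is not withdrawn. This stands as far as it goes. But step 5 covers what the year-only and month-and-year steps leave over, so it reads as the rule for dated events. No other SAP text tells a programmer how to classify a fully dated AE.
- *Worsening may already be a new AE.* Protocol 8.2.1 includes worsening of an existing medical condition in its AE definition, and each AE carries an onset date, so a post-dose worsening could have its own record, as in (b). This narrows the problem. Neither document says what a site does when an AE is already open at first dose, and the eCRF completion guide is not among the documents.
- *Verification is not replacement.* The SAP does not say that the date result wins, so it cannot be claimed that a correctly flagged worsening will be removed. Equally, it does not say that the flag wins.
- *The consequence is limited.* All AEs are listed, no hypothesis test depends on TEAE counts, and M207 application-site reactions can arise only after a patch is applied.
- *Counting unclear dates as treatment-emergent is cautious.* That is a fair default when timing is unknown. It does not justify counting an event whose recorded stop date shows that it ended before first dose.

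**Conclusion.** The gap is real but conditional. Steps 3 to 5 do not implement the worsening limb of protocol 8.2.1 and do not use the AE stop date. Where they decide, they give the wrong class for records such as (a), (c), (d) and (e). The result rests on two conditions: the occurrence type is blank or overridden, and, for the worsening error, the worsening stays under the original start date.

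Two stronger inferences are not supported. Affected events do not vanish from the report, because the loss is from summary tables and the listings keep them. Nor can a number of affected subjects be given. Multiplying the planned 250 by guessed rates of ongoing and worsening AEs would rest on figures the documents do not contain, and would ignore both conditions. The number is probably small. The point still merits correction, because a written rule for the primary safety tables departs from the protocol's own definition without declaring a change.

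**What to change.** In SAP 6.3, with a cross-reference in 11.2, before database lock:

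1. Define a TEAE as an AE with onset on or after first dose, or with earlier onset and increased severity on or after first dose.
2. Class any AE whose complete or partial stop date is clearly before first dose as not treatment-emergent, whatever its start date. Leave steps 3 and 4 as the default for the remaining partial dates.
3. State whether the eCRF occurrence type or the date rule prevails when they disagree.
4. State that worsening, after first dose, of an AE already open is entered as a new AE record with its own onset date, and put the same instruction in the eCRF completion guide.

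The cost is a few sentences in the SAP, one completion note and a small change to the derivation program. No new analysis is needed. If sites have already recorded worsening under original start dates, a query on AEs open at first dose would find those records.

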6.4. VISIT WINDOWS

Nominal Visits will be used in the analyses as reported on the eCRF. As per section 6.1, the subjects who withdraw/drop out from the study will have their ET visit data collected included in the analysis based on the closest visit window.

6.5. POOLING OF CENTRES

There will be no adjustment for multiple centers.

6.6. SUBGROUPS

No subgroups analysis will be performed.

7. DEMOGRAPHIC, OTHER BASELINE CHARACTERISTICS AND MEDICATION

7.1. SUBJECT DISPOSITION AND WITHDRAWALS

The number of subjects who were screened, entered run-in, entered the treatment phase, treated, completed 6 months, completed 12 months, and terminated from the study early will be summarized. The reasons for early termination of treatment or from the study will be summarized. Subjects who sign informed consent but do not enter the treatment phase will be listed along with failure type (screening or run-in) and reason for failure. Additionally, a summary of subjects present at each visit will be summarized. The number of subjects in each analysis population will be reported.

Inclusion/exclusion criteria definitions and violations will be listed. If no inclusion/exclusion criteria violations are reported, this will be noted in place of the listing.

7.2. DEMOGRAPHIC AND OTHER BASELINE CHARACTERISTICS

Demographic and baseline characteristic variables such as age, gender, race/ethnicity, height, and weight will be summarized using descriptive statistics. For categorical variables, frequencies and percentages will be presented. Continuous variables will be summarized using descriptive statistics (n, mean, median, SD, minimum, and maximum).

Age at Study day 1 = (Study day 1 visit date - date of birth + 1) / 365.25 and truncated to complete years.

Height (in cm) = height (in inches) * 2.54

Weight (in kg) = weight (in lbs) * 0.4536

BMI (kg/m²) = Weight (kg)/[Height(m)²].

Baseline characteristics, including medical history, Fitzpatrick skin scale results, migraine history, headache/migraine medication history and current drug or alcohol usage will also be summarized descriptively for the safety population.

7.3. MEDICAL HISTORY AND CONCOMITANT DISEASES

A summary table of the number and percentage of subjects by medical history system organ class (SOC) and preferred term (PT) will be produced using the safety population. Previous and concurrent diseases/conditions will be sorted alphabetically by SOC and PT using the Medical Dictionary for Regulatory Activities (MedDRA) coding dictionary, version 20.0 or higher. For the summary tables, a subject will be counted only once within preferred term if he/she experienced multiple episodes of the same event.

A separate by-subject listing for medical history data will also be provided.

7.4. OTHER BASELINE CHARACTERISTICS

The Fitzpatrick Skin Scale Questionnaire will be completed by the subjects at baseline will also be listed for each subject.

7.5. MEDICATION

All medications including Concomitant medications, prohibited medications, and Rescue Medications will be classified using the Anatomical Therapeutic Chemical (ATC) classification and preferred drug names from the World Health Organization Drug Dictionary (WHO-DD), version March 2016.

Summaries of medications will be presented in tabular form using the highest level ATC term as an upper classification and the preferred drug name as a lower classification level. All medications will be summarized and sorted by descending counts in the upper classification term and the lower classification term within the upper. For each subject, the medication will be counted only once within the upper classification level and only once within the lower classification level.

Separate listings will be provided for concomitant, prohibited, and rescue medications taken during the study separately.

7.5.1. Prior, Concomitant Medications, and Prohibited Medications

All medications taken within 30 days of screening and throughout the study, including over the counter medications, topical skin ointments and/or creams, prescription medications, herbal supplements, and/or vitamins will be reported as concomitant medications or prior medications.

Migraine prophylaxis medications are allowed if subjects have been on a stable dose for at least 30 days prior to screening and with no changes during the study.

Medications with ergot or another Triptan or vasoconstrictor drugs are prohibited on the day of the confirmed migraine prior to M207 application and for 24-hours post-administration of M207.

Aspirin, acetaminophen, NSAIDS, and other PRN or daily medications taken specifically for migraine symptoms are prohibited on the day of a confirmed migraine prior to M207 application and during the two hours following patch application.

Below is the list of all prohibited concomitant medications taken within 10 days prior to the Run-in Period and for the duration of this study (table 2):

Table 2: Prohibited Concomitant Medications

Drug Type	Medication
Monoamine oxidase inhibitors	Selegiline Tranlycypromine Isocarboxazid phenelzine
Selective serotonin reuptake inhibitors (SSRIs)	Paroxetine Fluoxetine Sertraline Citalopram Escitalopram Fluvoxamine
Serotonin-norepinephrine reuptake inhibitors (SNRIs)	Duloxetine Venlafaxine Desvenlafaxine Milnacipran Levomilnacipran
All Prescription Anticoagulants	Pradaxa Coumadin Eliquis Xarelto

Medications with a stop date before the treatment dosing date will be considered prior medications. Medications with a start or stop date on or after the treatment dosing date will be considered concomitant medications. All medications marked as ongoing are concomitant medications.

A medication with an incomplete stop date will be considered concomitant if

- Month is missing and year is equal to or after the year of treatment dosing date
- Day is missing and year is equal to the year of the treatment dosing date and month is equal to or after the month of the treatment dosing date.

All medications will be provided in a listing.

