3.2.5 Prior and Concomitant Medications Allowed During the Study

Medications that are considered necessary for the subject's welfare and are not specifically prohibited ([Section 6.2.11](#)), may be given at the discretion of the investigator. All medication(s) taken within 30 days prior to the screening visit and throughout the study must be recorded in the appropriate source document and in the case report form (CRF). Over the counter medications, topical skin ointments and/or creams, prescription medications, herbal supplements and/or vitamins will be recorded as concomitant medications.

Migraine prophylaxis medications are allowed if subjects have been on a stable dose for at least 30 days prior to screening and with no changes during the study.

Medications with ergot or another triptan or vasoconstrictor drugs are prohibited on the day of a confirmed migraine prior to M207 application and for 24-hours post-administration of M207.

Aspirin, acetaminophen, NSAIDS and other PRN or daily medications indicated specifically for migraine symptoms are prohibited on the day of a confirmed migraine prior to M207 application and during the two hours following M207 application.

Following M207 application, subjects will enter into the eDiary whether they took any medications (other than M207) for migraine symptoms prior to M207 application (on the day of application) or during the 48 hours post M207 application.

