4.2. SAFETY ENDPOINTS

- Changes from baseline in physical examination findings at Months 6 and 12
- Changes from baseline in vital signs at Months 1, 2, 3, 6, 9, 12, and at the 2-week post-study visit
- Changes from baseline in clinical laboratory parameters at Month 12
- Changes from baseline and/or shifts in 12-lead ECG parameters at Months 6 and 12
- Frequency of concomitant medications

- Incidence of treatment-emergent systemic and skin AEs (TEAEs)
- Frequencies of type of redness, severity of swelling, amount of bruising, and amount of bleeding (30 minutes only) at the application site as reported by the subject at 30 minutes, 2 hour, 12 hour, 24 hour, and 48 hours post-dose
- Frequencies of amount of skin itching and severity of pain at the application site as reported by the subject at 48 hours post-dose
- Frequencies of amount of bruising, erythema, and edema at the application site as assessed by the Investigator at Months 1, 2, 3, 6, 9, 12, and at the 2-week post-study visit
- Proportion of subjects with presence of skin signs and symptoms as assessed by the Investigator at Months 1, 2, 3, 6, 9, 12, and at the 2-week post-study visit

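### SAP 7.5.1: when only the stop day is missing, the concomitant-medication rule has no branch for a stop in a later calendar year

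*SAP*

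**What the plan says.** SAP 7.5.1 sorts all reported medications into prior or concomitant. Three general sentences come first:

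- For drugs finished earlier: "Medications with a stop date before the treatment dosing date will be considered prior medications".
- For drugs dated later at either end: "Medications with a start or stop date on or after the treatment dosing date will be considered concomitant medications".
- For drugs with no end yet: "All medications marked as ongoing are concomitant medications".

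A separate rule for partial stop dates follows, opening with "A medication with an incomplete stop date will be considered concomitant if". It has two bullets:

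- Month unknown: "Month is missing and year is equal to or after the year of treatment dosing date".
- Only the day unknown: "Day is missing and year is equal to the year of the treatment dosing date and month is equal to or after the month" in which dosing fell.

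SAP 6.3 step 4 deals with partial start dates differently. It compares month and year as one unit with those of the first dose and accepts anything the same or later.

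SAP 4.2 lists "Frequency of concomitant medications" as a safety endpoint. SAP section 17 gives prior and concomitant medications a table each (14.1.1.6 and 14.1.1.7).

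**The concern.** The two bullets do not match. With the month unknown, a later year is enough. With the month known, the year must be the dosing year itself. A more complete date can therefore get a worse answer than a less complete one, which cannot be what was meant.

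Treatment lasts up to twelve months, so for most subjects who complete it, it runs across a year end. The records exposed are background drugs begun before first dose and stopped during treatment. Migraine prophylaxis is one such group, and Protocol 3.2.5 allows it only on a "stable dose for at least 30 days prior to screening and with no changes during the study". If the bullets are coded alone, such a record is not flagged concomitant. It is not prior either, because it did not stop before dosing. The count behind a listed safety endpoint would then be short by those records.

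**Working it through.** The documents give no figure on this point, so there is none to reproduce. The check has two parts.

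**1. The bullets applied to an example.** Suppose first dose was on 15 November 2018 and the drug was started in 2017, so that its start date does not make it concomitant.

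| Recorded stop | Bullet that applies | Bullet met? | Position relative to first dose |
|---|---|---|---|
| October 2018, day missing | day-missing | No | Certainly before: correctly not concomitant |
| November 2018, day missing | day-missing | Yes | Uncertain: resolved to concomitant |
| December 2018, day missing | day-missing | Yes | Certainly after |
| February 2019, day missing | day-missing | **No** (2019 is not 2018) | **Certainly after**: earliest possible day is 1 February 2019 |
| 2019, month and day missing | month-missing | Yes | Certainly after |

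The February 2019 row is the gap. The month-missing bullet cannot help because the month is known. SAP 6.3 steps 3 to 5 cannot help because they test the start date, which precedes dosing.

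**2. How often an on-treatment stop could land there.** The inputs are Month 12 at Day 336 and Month 6 at Day 168 (schedule of procedures in both documents). My assumption is that first-dose dates are uniform over a 365-day year and stop days are uniform over treatment.

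Let d = 0, ..., 364 be the first-dose day, counted from 1 January, and L the treatment length in days. The treatment days falling in the next year number max(0, d + L − 365).

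- L = 336: the total over d is 1 + 2 + ... + 335 = 335 × 336 / 2 = 56,280. Divided by 365 × 336 = 122,640, this is 0.459.
- L = 168: the total is 167 × 168 / 2 = 14,028. Divided by 365 × 168 = 61,320, this is 0.229.
- Share of 336-day completers whose treatment crosses a year end: 335/365 = 0.918.

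For a single subject treated for 336 days, the share depends on the first-dose date: 0% for 15 January, 22% (75/336) for 15 April, 45% (152/336) for 1 July and 86% (289/336) for 15 November.

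I also enumerated every combination of dosing day and stop day. The bullets alone miss 45.9% of day-missing stops over 336 days and 22.9% over 168 days. They miss none of the month-missing stops. Every missed stop is certain to be after dosing. With month and year compared together, 0 of the 122,640 combinations are missed.

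**The case against.** The strongest reply is that SAP 7.5.1, read as a whole, already gives the right answer. The lead-in says if, not only if. A stop in a later year is after dosing whatever the day, so the general sentence makes it concomitant. The section also provides only two classes, and such a drug cannot be prior. On that reading, an error arises only if a programmer treats the day-missing bullet as exclusive and ignores the sentences above it.

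Much of this stands, and it rules out three stronger readings that a reader might infer:

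- **That the whole partial-stop-date rule is confined to the dosing year.** It is not. The month-missing bullet accepts later years.
- **That these records are certain to drop out of the tables.** The text does not say so. It supports two readings, and one of them keeps the records.
- **That efficacy or adverse-event results are affected.** No such analysis in the SAP uses the prior/concomitant flag. Rescue use comes from the eDiary (SAP 8.1.5), and treatment-emergence is decided from the timing of the event itself (SAP 6.3). Nor would the medication table reveal a mid-study stop, because it counts each drug once per subject (SAP 7.5). Stop dates belong to the by-subject listing (16.2.4.5).

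What the reply does not settle is which text governs a partial date. The bullets are not limited to uncertain cases: a later year in the first, and a later month of the same year in the second, are both certain to follow dosing. If the general sentence already covered such dates, that wording would be redundant. The bullets therefore read as the working rule for incomplete dates. A partial date cannot be compared directly with a full one, so code will tend to follow them.

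**Conclusion.** The gap is real, narrow and minor. It affects a record only if all of the following hold: the drug began before first dose, it is not marked ongoing, its stop date has month and year but no day, and the stop year is later than the dosing year. For such a record the partial-date bullets fail while the general sentence succeeds, so the classification depends on which one is programmed. If it is the bullets, the record is missing from the concomitant-medication summary.

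The effect on the summary cannot be sized, because the documents do not say how many stop dates lack a day. The 46% (336 days) and 23% (168 days) are shares of day-missing on-treatment stops under assumed uniform dates. They are not shares of all medications, and a reader should not take them as an error rate for the table. Actual enrolment dates could move the share a long way, as the 0% to 86% spread by first-dose date shows. All drugs remain in the listings under either reading.

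**What to change.** Reword the second bullet of SAP 7.5.1 along these lines: *day missing: concomitant when the stop month and year, taken together, are the same as or later than the month and year of the first dose date.* This brings it into line with SAP 6.3 step 4 and with the month-missing bullet. Naming the first dose date also helps because subjects dose repeatedly, so the treatment dosing date is not a single date.

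The cost is one SAP sentence and one line of code, made before database lock. No correctly classified record changes class.
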